## 1. INTRODUCTION

This statistical analysis plan (SAP) describes the statistical methods to be used during the reporting and analyses of data collected under Amgen Inc. Protocol 20130108, titled “A Randomized, Double-Blind Study to Compare Pharmacokinetics and Pharmacodynamics, Efficacy and Safety of ABP 798 with Rituximab in Subjects with Moderate to Severe Rheumatoid Arthritis.”

This SAP should be read in conjunction with the study protocol and electronic Case Report Forms (eCRFs). This version of the plan has been developed using the protocol version 4.0 dated 20 March 2018 and eCRFs version 5.0 dated 17 November 2016. Any further changes to the protocol or eCRFs may necessitate updates to the SAP.

The SAP is to be developed in two stages. The purpose is to “finalize” a SAP in order to start programming earlier in the process. Versions of the SAP up to initial sponsor approval will be known as SAP1. Changes following approval of SAP1 will be tracked in the SAP Change Log and a final version of the SAP, known as SAP2, will be issued for Amgen’s approval prior to unblinding for the final analysis.

## 2. STUDY OBJECTIVES

### 2.1 PRIMARY OBJECTIVES

The primary objective for this study is to demonstrate pharmacokinetic (PK) similarity (as assessed principally by area under the serum concentration-time curve [AUC] from time 0 extrapolated to infinity [AUCinf] and the maximum observed serum concentration [Cmax], following the 2nd infusion of the 1st dose) of ABP 798 following 2 intravenous (IV) infusions of 1000 mg each, relative to that of 2 IV infusions of 1000 mg each of rituximab (US) and of rituximab (EU).

### 2.2 SECONDARY OBJECTIVES

The secondary objectives are:

- to demonstrate PK similarity between rituximab (US) and rituximab (EU) as assessed by AUCinf and by Cmax after second infusion of the first dose
- to assess the clinical efficacy of ABP 798 compared with rituximab
- to assess the safety and immunogenicity of ABP 798 compared with rituximab.

## 3. STUDY DESIGN

This is a randomized, double-blind, active-controlled 3-arm study in adult subjects with moderate to severe Rheumatoid Arthritis (RA) who have an inadequate response or intolerance to other disease-modifying anti-rheumatic drugs (DMARDs), which must include intolerance or inadequate response to one or more tumor necrosis factor (TNF) inhibitor therapies.

Sponsor: Amgen Inc.

Statistical Analysis Plan

Protocol No: 20130108

10-December-2018/ Version 2.0

---

Approximately 300 subjects (100 per treatment group) will be enrolled. The subjects will be randomized to receive either 2 IV infusions of ABP 798, 1000 mg each, given 2 weeks apart (treatment group A), or 2 IV infusions of rituximab (US) 1000 mg each, given 2 weeks apart (treatment group B) or 2 IV infusions of rituximab (EU), 1000 mg each, given 2 weeks apart (treatment group C) in a double blind fashion. A total of 2 doses will be administered during the study; each dose consists of 2 infusions, 2 weeks apart.

An independent data monitoring committee (DMC) will evaluate the safety data throughout the study, including an initial safety analysis after the first 18 subjects have received the first dose (1000 mg x 2 infusions of either ABP 798 or rituximab (EU) or rituximab (US)).

At week 24, the subjects in treatment groups A and C will continue with and receive the second dose of the same treatment, and the subjects in treatment group B will transition to treatment group A1 and receive ABP 798 1000 mg x 2 as their second dose.

Retreatment may occur earlier, i.e., anytime from week 16 to week 24, in individual subjects, if necessary in the opinion of the Investigator.

The end of study (EOS) will be at week 48 (or 24 weeks after the first infusion of second dose for subjects retreated before week 24), and a final analysis will be performed when all subjects have completed or have had the opportunity to complete the week 48/EOS assessments.

See [Figure 1](#) below for a summary of the study design.

[figure not shown]

Sponsor: Amgen Inc.

Statistical Analysis Plan

Protocol No: 20130108

10-December-2018/ Version 2.0

**Figure 1 Study Diagram**

\* Retreatment will begin at week 24 or earlier, i.e., anytime from week 16 to week 24 in individual subjects if necessary in the opinion of the Investigator.

### 3.1 SAMPLE SIZE CONSIDERATIONS

Approximately 300 subjects will be randomized in a 1:1:1 ratio to receive ABP 798, rituximab (US), or rituximab (EU), stratified by geographic region (North America, Eastern Europe, and Western Europe), seropositivity (rheumatoid factor (RF)-positive and/or anti-cyclic citrullinated peptide (CCP)-positive vs. RF-negative and CCP-negative), and number of prior biologic therapies used for RA (1 vs. >1). The sample size will provide > 90% power to demonstrate similarity on the primary PK endpoints based on an assumption of between-subject variability (as measured by coefficient of variation) of 40%, true geometric mean ratio (GMR) of 1 among ABP 798, rituximab (US), or rituximab (EU), a margin of (0.8, 1.25) and 15% dropout by week 24. PK similarity will

Sponsor: Amgen Inc.

Statistical Analysis Plan

Protocol No: 20130108

10-December-2018/ Version 2.0

be tested between ABP 798 versus rituximab (US) and ABP 798 versus rituximab (EU), each with a significance level of 0.05. The similarity between rituximab (US) and rituximab (EU) will be evaluated as well.

With the planned sample size, there is 94% probability that the 90% CI of the difference between the ABP 798 arm and the pooled rituximab (rituximab [EU] and rituximab [US]) arm and 83% probability that the 90% CI of the difference between test (ABP 798) and reference (rituximab [EU] or rituximab [US]) in DAS28-CRP change from baseline at week 24 will fall into the equivalence margin of  $\pm 0.6$  (EULAR response criteria), assuming a standard deviation of 1.4 ([Volkmann et al, 2010](#)) and true mean difference of 0.

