Clinical equivalence will be evaluated for DAS28-CRP at week 24 using the Full Analysis Set consisting of all randomized subjects. **If PK similarity is established between rituximab (US) and rituximab (EU), the 2 arms will be combined into a single reference arm for the primary assessment of clinical equivalence between ABP 798 and rituximab. The results for ABP 798 vs. rituximab (EU) and ABP 798 vs. rituximab (US) will be provided for descriptive purposes. If PK similarity is not established, the ABP 798 arm will be compared to each of the individual rituximab arms separately to establish clinical equivalence of ABP 798 to the individual reference arms.**

With the planned sample size, there is **94% probability that the 90% CI of the difference between the ABP 798 arm and the pooled rituximab (rituximab[EU] and rituximab[US]) arm and 83% probability that the 90% CI of the difference between test (ABP 798) and reference (US-licensed rituximab or EU-authorized rituximab) in DAS28-CRP change from baseline at week 24 will fall into the equivalence margin of ± 0.6 (EULAR response criteria), assuming a standard deviation of 1.4 (Volkmann et al, 2010).** **DAS28-CRP at other timepoints and ACR20, 50 and 70 will be summarized descriptively.**

In addition, all categorical variables will be summarized using the number and percent of subjects falling into each category and all continuous variables will be summarized using mean, standard error or standard deviation, median, minimum, maximum, and number of subjects. Safety endpoints will be summarized descriptively as well, based on all randomized subjects who received at least one infusion of IP (ie, Safety Analysis Set).

DATE AND VERSION: 20 March 2018; Version 4.0

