8.4.3.3 Replacement of Subjects

Subjects who are withdrawn will not be replaced. However, sufficient subjects will be included to ensure the minimum sample size defined (see [Section 12.2](#)).

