### 9.7.1 DAS28-CRP

#### PRIMARY STATISTICAL ANALYSIS

##### **DAS28-CRP at Week 24**

The analyses will be performed on the FAS based on the day 1 through week 24 time period described above, with observed data. Subjects with missing baseline DAS28-CRP will not be included in the analysis since no change from baseline can be calculated. Analyses will assess the hypothesis that there are no clinically meaningful differences between ABP 798 and rituximab arms in DAS28-CRP change from baseline at week 24. This primary efficacy endpoint will be tested by comparing the 2-sided 90% CI of the change from baseline at week 24 of DAS28-CRP between ABP 798 and rituximab arms with an equivalence margin of (-0.6, 0.6).

To evaluate treatment differences across time points at which DAS28-CRP was assessed, repeated-measures analysis will be utilized for the day 1 through week 24 time period described above. Data from all assessed postbaseline time points will be included in the analysis. Besides stratification variables, baseline DAS28-CRP value, visit (week), treatment, and treatment-by-visit interaction will be included in the models, with visit as a categorical variable. The adjusted mean with 95% CI for each arm and 90% and 95% CIs for the mean difference will be constructed for mean difference of DAS28-CRP change from baseline between ABP 798 and rituximab arms at each time point.

The mixed model repeated measures analysis will be implemented using PROC MIXED in SAS. Because the time points at which measurements occur are not equally spaced (8, 12, and 24 weeks) and because measurements over time are expected to be correlated, with correlation coefficients being greater for time points that are closer together, a

Sponsor: Amgen Inc.

Statistical Analysis Plan

Protocol No: 20130108

10-December-2018/ Version 2.0

spatial covariance structure denoted SP(POW) in SAS will be used. However, before implementing this structure, its appropriateness will be checked by choosing the smaller Akaike's information criterion when comparing the SP(POW) covariance structure with unstructured covariance structure. Example code for PROC MIXED with three treatment groups is displayed below:

CCI

Note: The contrasts in the lsmeestimate statement may need to be changed depending on the order of the treatments. Only the individual arm comparison SAS code is presented.

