#### 9.7.4 Methods for Handling Dropouts and Missing Data for Efficacy

For ACR, the determination of ACR20/50/70 response will be based on the data available at each visit (refer to [Appendix 2](#) for handling missing ACR individual components), taking into account prorated tenderness and swollenness of joints.

For the primary DAS28-CRP analysis, the primary repeated measures model will be fit to the observed data. The rate of missing DAS28-CRP at week 24 will be tabulated with reasons, such as missing baseline, incomplete week 24 assessment (missing up to 3 of 4 components), outside of the defined week 24 analysis time frame, missing week 24 component assessments (missing all 4 components), and discontinued from the study early prior to week 24 (day 210).

Tipping point analyses will be performed for the efficacy endpoints of DAS28-CRP change from baseline at week 24 based on ANCOVA model using FAS analysis set to explore the sensitivity of results to violations in assumptions about the missing data (i.e., to various missing not-at-random assumptions). Assumptions (tipping point) under which the 90% CI no longer rules out unacceptable differences in efficacy as determined by DAS28-CRP change from baseline at week 24 between ABP 798 and reference (Rituximab (US) and Rituximab (EU)) will be identified.

In this analysis, all the observed data will be included as non-missing, regardless of adherence to treatment or use of prohibited medication. The analysis will be performed using a general three-step approach:

(1) Multiple imputation will be done using PROC MI to generate multiple (e.g., 10) imputed datasets by imputing missing data assuming monotone missing pattern and that subjects with missing data have, on average, worse or better efficacy compared to those who have values. The mean difference between the (unobserved) missing values and observed values (refer to as shift) can vary independently for the different treatment groups. For this analysis, the shifts for Rituximab(EU) and Rituximab(US) are assumed to be the same.

(2) Each of these imputed datasets (which contains identical values of non-missing data but different values imputed for missing data) is analyzed using standard SAS procedure, e.g., PROC GLM, PROC GENMOD, etc.

(3) Results from all imputed datasets are then combined together for overall inference using PROC MIANALYZE.

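### The 94% and 83% DAS28-CRP equivalence probabilities assume complete week-24 data, although the same SAP section plans 15% dropout by week 24

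*SAP*

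**What the plan says.** SAP 3.1 has two paragraphs. The first concerns the primary PK endpoints. It bases power above 90% on a CV of 40%, a true ratio of 1, "a margin of (0.8, 1.25) and 15% dropout by week 24". The second concerns DAS28-CRP change from baseline at week 24. It says "there is 94% probability that the 90% CI of the difference between the ABP 798 arm and the pooled rituximab" arm will lie within ±0.6, and gives "83% probability that the 90% CI of the difference between test (ABP 798) and reference" for a single rituximab arm. Its inputs are the planned sample size, an SD of 1.4 and a true mean difference of 0. It states neither a dropout rate nor an evaluable number.

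The same pair stands in the Protocol synopsis ("94% probability that the 90% CI of the difference between the ABP 798 arm and the pooled rituximab") and in Protocol 12.6.6, again without dropout. In the body of the Protocol the 15% appears in section 12.2, within the PK power statement.

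Three other provisions bear on how many subjects will have a week-24 value:

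- Protocol 8.4.3.3: "Subjects who are withdrawn will not be replaced". Its next sentence refers to including enough subjects to reach the minimum in section 12.2, which is about 300 randomized.
- SAP 9.7.4: "For the primary DAS28-CRP analysis, the primary repeated measures model will be fit to the observed data". The same section lists early discontinuation among the reasons for a missing week-24 value.
- SAP 9.7.1, on the primary model: "Besides stratification variables, baseline DAS28-CRP value, visit (week), treatment, and treatment-by-visit interaction will be included in the models".

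**The concern.** The two paragraphs of SAP 3.1 describe the same subjects at the same visit but appear to use different evaluable numbers, and the reader is not told. PK power allows for the loss of 15 in 100 by week 24. The efficacy probabilities, for an endpoint measured at week 24, do not seem to allow for any.

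If so, the chance that a truly identical product meets the margin is overstated under the plan's own dropout assumption. The single-reference figure matters most. It applies if PK similarity between rituximab (US) and rituximab (EU) is not established, because ABP 798 is then compared with each arm separately. What is at stake is the accuracy of a planning figure for a secondary objective, although SAP 4.2.2 names this the primary efficacy endpoint and SAP 9.7.1 tests it formally against a margin.

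**Working it through.** **Inputs from the documents**

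- 100 randomized per arm, so 100 vs 200 when the reference arms are pooled (SAP 3 and 3.1).
- SD 1.4 and true difference 0 (SAP 3.1).
- Margin ±0.6, two-sided 90% CI (SAP 9.7.1). This is two one-sided tests at 0.05 each.
- Dropout of 15% by week 24 (SAP 3.1, Protocol 12.2). 100 × 0.85 = 85 per arm, or 85 vs 170 pooled.

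**Formula**

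SE = 1.4 × √(1/n₁ + 1/n₂). In the normal approximation, the probability that the 90% CI lies within the margin at zero true difference is 2Φ(0.6/SE − 1.645) − 1. The exact version uses the t critical value on n₁ + n₂ − 2 degrees of freedom and integrates over the distribution of the estimated SD.

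**Step 1: reproduce the printed figures (all 100 per arm evaluable)**

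- Pooled, 100 vs 200: SE = 1.4 × √0.015 = 0.1715; 0.6/0.1715 = 3.499; 3.499 − 1.645 = 1.854; probability 93.6% (exact 93.5%). Printed: 94%.
- Single, 100 vs 100: SE = 1.4 × √0.02 = 0.1980; 0.6/0.1980 = 3.030; 3.030 − 1.645 = 1.386; probability 83.4% (exact 83.1%). Printed: 83%.

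Both agree, with no room for loss at SD 1.4. At 99 per arm the exact pooled value is 93.3%, which would be printed as 93%. Other readings do not give both figures. A one-sided 0.05 test at 85 per arm gives 94.3% pooled but 87.5% single. A 95% CI at 100 per arm gives about 87% and 71%.

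**Step 2: apply the section's own 15% dropout**

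- Pooled, 85 vs 170: SE = 1.4 × √(1/85 + 1/170) = 0.1860; 0.6/0.1860 = 3.226; 3.226 − 1.645 = 1.581; probability 88.6% (exact 88.4%).
- Single, 85 vs 85: SE = 1.4 × √(2/85) = 0.2148; 0.6/0.2148 = 2.794; 2.794 − 1.645 = 1.149; probability 75.0% (exact 74.5%).

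The expected half-width of the 90% CI (1.645 × SE) rises from 0.28 to 0.31 pooled, and from 0.33 to 0.35 against a single arm.

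**Step 3: allow for recovered precision**

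The documents give no correlation, residual SD or capture rate, so the rows beyond the first two rest on assumptions. The residual SD is taken as 1.4 × √(1 − r²).

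| Scenario | Pooled | Single |
|---|---|---|
| Complete data, SD 1.4 | 93.5% | 83.1% |
| 85 per arm, SD 1.4 | 88.4% | 74.5% |
| Half of dropouts have an in-window value (92.5 per arm), SD 1.4 | 91.3% | 79.2% |
| 85 per arm, r = 0.3 (SD 1.336) | 91.6% | 79.7% |
| 85 per arm, r = 0.4 (SD 1.283) | 93.8% | 83.6% |

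To reach the complete-data values with 85 per arm, the residual SD would have to be about 1.29 instead of 1.4.

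**Step 4: the PK claim for comparison**

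A CV of 40% gives a log-scale SD of √ln(1.16) = 0.385, and the margin is ln(1.25) = 0.223. With 85 per arm the exact power is 96.6% per comparison for one endpoint. The PK statement therefore holds after dropout.

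**The case against.** The strongest reply is that nothing has been miscalculated. The efficacy sentence refers to the planned sample size, the figures reproduce at that size, and the 15% belongs grammatically to the PK sentence. That is correct as a description of the arithmetic: the defect is an unstated assumption. It does not remove the inconsistency, because dropout by week 24 removes the same subjects from a week-24 efficacy endpoint.

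The second reply is that a completers calculation is not the planned analysis. The repeated-measures model adjusts for baseline and uses weeks 8 and 12. Withdrawn subjects are asked for the week 48/EOS assessments within 14 days (Protocol 8.4.3.2), and an assessment on days 106 to 210, on or before retreatment, can count as week 24 (SAP 5.1). Combining two of the assumptions above (92.5 per arm and r = 0.3) gives about 93.9% and 83.8%, close to the printed pair. This stands as a qualification: 88% and 74–75% are the low end of the range considered at zero true difference. But the plan states an SD of 1.4 and no precision gain, so it cannot rely on one silently.

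The third reply is limited consequence. Efficacy is a secondary objective, the sample size is driven by PK, and the single-reference comparison governs only if PK similarity of the two reference products is not shown. Protocol version 4.0 and the SAP are also both dated after the planned study end of 28 February 2018. All of this is true. It bears on how much the error matters, not on whether the figures are right as printed.

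The second sentence of Protocol 8.4.3.3 does not help either. The minimum it points to is the number randomized, not the number evaluable.

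**Conclusion.** The concern holds. At the stated SD, margin and zero difference, 94% and 83% require every randomized subject to be evaluable at week 24, and the documents nowhere say so. With the section's 15% dropout and no covariate gain, the probabilities are about 88% and 74–75%, roughly 5 and 8–9 points lower. The chance of missing the margin for identical products is up to about 12% (pooled) or 26% (single reference), against the implied 6% and 17%. The pooled comparison stays comfortably above 80%; the single-reference fallback does not.

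The lower pair rests on two assumptions: that the 15% dropout translates fully into missing week-24 values, and that the repeated-measures model leaves the SD at 1.4. Both are conservative. The equivalence decision uses the observed 90% CI, so type I error, PK power and the analysis itself are unaffected. The point should be corrected, but it concerns a planning figure.

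**What to change.** In SAP 3.1, Protocol 12.6.6 and the Protocol synopsis, label the present figures and add the adjusted ones, for example: *Assuming complete week-24 data, 94% (pooled) and 83% (single reference); allowing for 15% dropout by week 24 (85 evaluable per arm, SD 1.4, no covariate adjustment), about 88% and 74–75%.* If the sponsor wishes to rely on precision gained from the repeated-measures model, state the residual SD used and its source; about 1.29 would be needed to keep the printed figures at 85 per arm.

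This changes wording in three places. It adds no patients and leaves the endpoint, margin and analysis as they are; the stated probabilities become less favourable. Protocol 15.2 requires any Protocol change to be made by amendment, so the two Protocol edits carry that administrative step.

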### 3.2 RANDOMIZATION

Approximately 300 subjects will be randomized in a 1:1:1 ratio to receive either ABP 798, rituximab (US), or rituximab (EU) via an Interactive Voice or Web Response System (IXRS), stratified by geographic region (North America, Eastern Europe, and Western Europe), seropositivity (RF-positive and/or CCP-positive vs. RF-negative and CCP-negative), and number of prior biologic therapies used for RA (1 vs.  $>1$ ).

Assignment to the treatment arms will be based on a computer-generated randomization schedule created before the start of the study. The randomization schedule will be prepared by a statistician not involved in the conduct of the study.

A third party vendor, [PPD](#), will be responsible for generating the randomization scheme and managing the randomization activities of this study.

## 4. STUDY VARIABLES AND COVARIATES

### 4.1 PRIMARY VARIABLE

- The primary PK endpoints are the  $AUC_{inf}$  and  $C_{max}$  following the 2nd infusion of 1st dose.

### 4.2 SECONDARY VARIABLES

#### 4.2.1 Pharmacokinetic

The secondary PK endpoints will include:

- $AUC$  from time 0 on day 1 prior to the 1st infusion of the 1st dose to 14 days postdose ( $AUC_{0-14\ day}$ )
- $AUC$  from time 0 on day 1 prior to the 1st infusion of the 1st dose to week 12 ( $AUC_{0-12\ wk}$ )
- $C_{max}$  following the 1st infusion of the 1st dose.

Sponsor: Amgen Inc.

Statistical Analysis Plan

Protocol No: 20130108

10-December-2018/ Version 2.0

- Additional PK endpoints including the time of  $C_{max}$  ( $t_{max}$ ), last measurable serum concentration after the second infusion up to week 12 ( $C_{last}$ ), terminal elimination half-life ( $t_{1/2}$ ), the terminal elimination rate constant ( $\lambda_z$ ), clearance (CL), mean residence time (MRT), percent of AUC extrapolation (% $AUC_{extrap}$ ), and  $AUC_{0-12}$  wk/ $AUC_{inf}$ .

#### 4.2.2 Efficacy

The efficacy endpoints include:

Primary efficacy endpoint:

- Disease activity score (DAS) 28-CRP change from baseline at week 24.

Secondary efficacy endpoints:

- DAS 28-CRP change from baseline at week 8, 12, 40 and 48.
- ACR20, ACR50 and ACR70 at weeks 8, 12, 24, 40 and 48.
- Hybrid ACR at weeks 8, 12, 24, 40 and 48.

#### 4.2.3 Pharmacodynamic

Pharmacodynamic (PD) endpoints will include the percent of subjects with complete depletion in CD19+ cell count from day 1 to day 3 and duration of CD19+ B-cell complete depletion.

